### 5.3.2 Primary Efficacy Endpoint

#### Objective Response Rate (ORR)

ORR is the proportion of patients whose BOR is CR or PR. Various ORRs, based on Per Investigator Assessment BOR, Per Sponsor Derivation BOR with confirmation, and Per Sponsor Derivation BOR without confirmation as described in Section 5.3.1, will be estimated using count, percentage and exact (Clopper-Pearson) 95% CI.

### 5.3.3 Secondary Efficacy Endpoints

#### Progression-Free Survival (PFS)

PFS is defined as the number of months from the treatment start date to the date of documented disease progression or death due to any cause. PFS of living patients without documented PD will be censored at the time of last tumor assessment or the date of first treatment if there is no post-baseline tumor assessment.

Distribution of PFS will be estimated using the Kaplan-Meier method in the Evaluable Population. The median and quartiles of PFS and the PFS rate at 3, 6, 9 and 12 months will be reported with corresponding 95% CI.

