#### 3.3.2 Follow-up Tumor Assessments

**Target lesions** are followed by tumor size, longest diameter of TLs and short axis of LNs, and SOD are calculated for response evaluation. At each tumor assessment, the tumor response of **target lesions** is determined as below.

- **Complete Response (CR):** disappearance of all target TLs and all target LNs with short axis <10mm
- **Partial Response (PR):**  $\geq 30\%$  decrease in SOD from **Baseline**, and not PD (see below)
- **Progressive Disease (PD):**  $\geq 20\%$  increase in SOD from previous smallest SOD on study, and an absolute increase of  $\geq 5\text{mm}$
- **Stable Disease (SD):** SOD change neither sufficient for PR nor sufficient for PD
- **Not Evaluable (NE):** not all target lesions evaluated, and evaluated lesions not sufficient for PD

**Non-target lesions** are assessed qualitatively with present, absent or unequivocal progression and tumor response is determined as below.

- **Complete Response (CR):** disappearance of all non-target TLs, normalization of tumor marker level, and all non-target LNs with short axis <10mm
- **Non-CR/Non-PD:** persistence of any non-target lesion and/or maintenance of abnormal tumor marker level
- **Progressive Disease (PD):** unequivocal progression (substantial worsening) of existing non-target lesions
- **Not Evaluable (NE):** not all non-target lesions evaluated
- **Not Applicable (NA):** no non-target lesions identified at **Baseline**

**New lesions** are tumor lesions that were not present at **Baseline**. The finding of a new lesion should be unequivocal, and the appearance of new malignant lesions denotes disease progression.

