### 3.3.3 Time Point Response at Each Tumor Assessment

As summarized below, the time point response at each follow-up tumor assessment are determined according to the evaluation of target lesions, non-target lesions, and new lesions.

Table 1. Determination of Time Point Response

Target Lesions	Non-Target Lesions	New Lesions	Time Point Response
CR	CR or NA	No	CR
CR	Non-CR/Non-PD or NE	No	PR
PR	Any but PD	No	
SD	Any but PD	No	SD
PD	Any	Yes or No	PD
Any	PD	Yes or No	
Any	Any	Yes 	
NE	Any but PD	No	NE

 If the finding of new lesion is equivocal, it should be confirmed from next scan.

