#### 4 ANALYSIS POPULATIONS

Two analysis populations have been defined as follows:

- The **Evaluable Population (EP)** consists of all patients who are enrolled, complete at least one cycle of poziotinib treatment, and have at least one evaluable post-baseline tumor response evaluation using RECIST criteria, Version 1.1.
- The **Safety Analysis Population (SAF)** includes all patients who signed informed consent, enrolled, and received at least one dose of study treatment. All demographics, Baseline characteristics, and safety data will be analyzed using the **SAF** population.

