**Time to Progression (TTP)**

TTP is defined as the number of months from the first dose of study drug to tumor progression, which excludes death without tumor progression, by the end of study. TTP of patients who die without documented PD will be censored at date of death. TTP of living patients without documented PD is censored at the same time as PFS, which is the last tumor assessment or the date of first treatment if there is no post-baseline tumor assessment.

Distribution of TTP will be estimated using the Kaplan-Meier method in the Evaluable Population. The median and quartiles of TTP and the TTP rate at 3, 6, 9 and 12 months will be reported with corresponding 95% CI.

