**Duration of Response (DoR)**

DoR will be evaluated only for patients whose BOR is CR or PR and is defined as the time (in months) from the date that response evaluation criteria are first met for CR or PR (whichever status is recorded first) until the first subsequent date that PD or death is documented. DoR of patients without documented PD or death will be censored at the time of last tumor assessment.

Distribution of various DoRs will be estimated using the Kaplan-Meier method. The median and quartiles of DoR and the DoR rate at 3, 6, 9 and 12 months will be reported with corresponding 95% CI.

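### The PFS, TTP and DoR censoring rules do not say that the last tumor assessment must be evaluable, so a final Not Evaluable scan can set the censoring date

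*SAP*

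**What the plan says.** SAP 5.3.3 gives three censoring rules that depend on the date of the last scan.

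- PFS: "PFS of living patients without documented PD will be censored at the time of last tumor assessment". If there is no post-baseline assessment, the date of first treatment is used.
- TTP, living patients: "TTP of living patients without documented PD is censored at the same time as PFS, which is the last tumor assessment", with the same fallback.
- DoR: "DoR of patients without documented PD or death will be censored at the time of last tumor assessment".

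For TTP there is a separate rule for deaths: "TTP of patients who die without documented PD will be censored at date of death".

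SAP 3.3.2 defines NE for target lesions as "not all target lesions evaluated, and evaluated lesions not sufficient for PD". SAP 3.3.3 says that "the time point response at each follow-up tumor assessment are determined according to the evaluation of target lesions, non-target lesions, and new lesions", and its table includes NE as one of the outcomes.

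SAP 4 does use the qualifier that the censoring rules lack. A patient enters the Evaluable Population (EP) only on condition that they "have at least one evaluable post-baseline tumor response evaluation". SAP 5.3.1 likewise deals with NE visits when it derives best overall response. SAP 5.1.2 says only that missing data are not imputed, and Protocol 8.5.2 gives no censoring rule.

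**The concern.** In the SAP's own terms an NE visit is a tumor assessment, because it receives a time point response. If it is a patient's last visit, the unqualified wording makes its date the censoring date. The patient is then counted as at risk and progression-free up to a scan on which not all target lesions were evaluated.

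Patients who leave without progression are to be expected here. SAP 3.3 ends tumor assessments at intolerable adverse events, and the SAP's summary of changes says the starting dose was not well tolerated. The 3-, 6-, 9- and 12-month rates are estimated in small cohorts (33 and 34 enrolled, SAP 3), so a few censoring dates can move them. Two programmers could also read the rule differently and produce different dates from the same data.

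**Working it through.** The plan states no figure for this point, so there is nothing to reproduce. The check covers who is affected, the direction and the size.

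**Who is affected.** Only patients without documented PD whose final scan was NE and who are alive (for TTP and PFS) or have no recorded death (for DoR). An NE scan followed by an evaluable scan, by PD, or by a death that counts as an event does not set a censoring date.

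**Extra time per patient.** Scans are every 6 weeks ±14 days (SAP 3.3). One trailing NE scan adds nominally 42 days (42/30.44 = 1.38 months). If the two scans fall at opposite ends of their windows, the range is 42 − 28 = 14 to 42 + 28 = 70 days.

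**Direction.** The Kaplan-Meier estimate is S(t) = ∏(1 − d/n) over event times up to t. A later censoring date leaves every d unchanged and leaves each n the same or larger. No factor can fall, so the curve stays level or rises.

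**Mechanism at one scan (assumed counts).** Take 20 patients at risk, of whom 6 have PD and 2 have NE as their last scan.

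- All scans on the same day, NE patients counted at risk: drop = 6/20 = 30.0%.
- NE patients censored at their previous evaluable scan: drop = 6/18 = 33.3%.
- PD and NE dates in random order within the scan window, NE patients at risk until their own date: averaged over the 28 possible placements of the 2 NE dates among the 8, drop = 31.8%.

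The 3.3-point gap needs tied dates. With dates spread over the window it is 33.3 − 31.8 = 1.5 points.

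**Size over follow-up (simulation, 100,000 patients per scenario).** The documents supply the scan interval, the ±14-day window and the 24-month limit. The following are assumptions, because the documents give no values: exponential times, median TTP 3, 5 or 8 months, median time to dropout 6 or 12 months, median time to death without PD 12 or 24 months, and one trailing NE scan in 10% or 30% of patients who leave alive without PD.

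Selected 6-month progression-free rates, with median time to death without PD of 12 months:

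| Median TTP | Median dropout | NE share | Last evaluable scan | NE scan counted | Difference |
|---|---|---|---|---|---|
| 3 mo | 6 mo | 30% | 0.233 | 0.251 | +1.8 points |
| 5 mo | 6 mo | 10% | 0.421 | 0.427 | +0.6 |
| 5 mo | 6 mo | 30% | 0.420 | 0.439 | +1.9 |
| 8 mo | 12 mo | 10% | 0.589 | 0.591 | +0.2 |
| 8 mo | 12 mo | 30% | 0.596 | 0.604 | +0.8 |

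Over all 24 scenarios the difference was +0.2 to +1.9 points.

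With median TTP of 5 or 8 months, the estimated median rose by 0.03 to 0.29 months. With median TTP of 3 months it rose by 0.01 to 0.53 months. The larger jumps there occur because the median crosses the gap between two scan windows: day 98 (84 + 14, 3.22 months) to day 112 (126 − 14, 3.68 months).

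**Against sampling error.** For a 6-month rate of 0.42 in 33 patients, ignoring censoring, the 95% half-width is 1.96 × √(0.42 × 0.58/33) = 0.168, about 17 points.

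**The case against.** **The SAP nowhere says that an NE scan counts.** This stands. The reading comes from unqualified wording taken together with SAP 3.3.2 and 3.3.3, and a programmer could reasonably use the last evaluable scan. The supportable statement is that the rule permits NE dates and does not settle the matter.

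**An NE visit is not empty.** This also stands. Under the SAP 3.3.3 table a time point is NE only if the target lesions that were read do not show PD, non-target status is not PD and there is no new lesion. A reader might infer that patients are credited with time for which there is no evidence at all. The table does not support that: the evidence is incomplete, because some target lesions are unread and non-target status may itself be NE.

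**The TTP death-date rule.** A reader might infer that it is a second source of inflation for all three endpoints. It is not. Death is an event for PFS and DoR, so the rule touches TTP only. Censoring at death is also consistent with the Protocol 8.5.2 definition, which leaves out death without progression. In a simulation of 6,000 patients with scans exactly every 42 days and 5% to 20% dying between progression and the next scan, the TTP curve was the same under either date. With scan dates staggered as above, the death date added 0.6 to 1.5 points to the 6-month TTP rate under the assumed death rates. It is a defensible choice.

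**Small and descriptive.** The shift is well inside sampling error, Protocol 8.1 rules out hypothesis testing, and no decision threshold is tied to these endpoints. This stands and sets the severity. It does not remove the case for a one-phrase correction, because the shift is systematic and in one direction.

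**Conclusion.** The point holds as a minor one. SAP 5.3.3 omits the evaluable qualifier that SAP 4 applies to the EP and SAP 5.3.1 takes into account for best overall response. Followed as written, it lets a trailing NE scan extend follow-up by about one scan interval, and the curve can only stay level or rise.

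The size is about 0.2 to 2 points on the 6-month rate. It rests on the assumed 10% to 30% NE share and the assumed progression, dropout and death rates. The direction needs none of these assumptions.

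A reader might go further and infer that the reported efficacy is materially overstated. The documents do not support that: PFS, TTP and DoR are secondary and descriptive, and ORR does not use these dates.

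**What to change.** In the PFS, TTP (living patients) and DoR paragraphs of SAP 5.3.3, change the censoring date to the *last evaluable tumor assessment (time point response other than NE)*.

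State whose time point response decides this. SAP 5.3.1 has both an investigator and a sponsor-derived response, and they can differ. Use the same source as for the PD date; otherwise the new wording is ambiguous too.

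The rule is always workable in the EP, where every patient must "have at least one evaluable post-baseline tumor response evaluation using RECIST criteria, Version 1.1", provided that the same source decides EP membership. The fallback to the date of first treatment then never applies and can be deleted or marked as not applicable.

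The TTP rule for deaths can stay. At most, add a sensitivity analysis that censors those deaths at the last evaluable assessment.

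The cost is SAP wording and a small programming change. The estimates may become slightly less favourable.

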**Disease Control Rate (DCR)**

DCR is the proportion of patients whose BOR is CR, PR, or SD. Various DCRs, based on Per Investigator Assessment BOR, Per Sponsor Derivation BOR with confirmation, and Per Sponsor Derivation BOR without confirmation as described in Section 5.3.1, will be estimated using count, percentage and exact (Clopper-Pearson) 95% CI.

**Time to Progression (TTP)**

TTP is defined as the number of months from the first dose of study drug to tumor progression, which excludes death without tumor progression, by the end of study. TTP of patients who die without documented PD will be censored at date of death. TTP of living patients without documented PD is censored at the same time as PFS, which is the last tumor assessment or the date of first treatment if there is no post-baseline tumor assessment.

Distribution of TTP will be estimated using the Kaplan-Meier method in the Evaluable Population. The median and quartiles of TTP and the TTP rate at 3, 6, 9 and 12 months will be reported with corresponding 95% CI.

**Duration of Response (DoR)**

DoR will be evaluated only for patients whose BOR is CR or PR and is defined as the time (in months) from the date that response evaluation criteria are first met for CR or PR (whichever status is recorded first) until the first subsequent date that PD or death is documented. DoR of patients without documented PD or death will be censored at the time of last tumor assessment.

Distribution of various DoRs will be estimated using the Kaplan-Meier method. The median and quartiles of DoR and the DoR rate at 3, 6, 9 and 12 months will be reported with corresponding 95% CI.

**5.3.4 Subgroup Analysis**

Analysis of the primary and selected secondary efficacy endpoints will be performed for the following subgroups:

- patients by total lines of prior therapy (2 lines, 3 lines,  $\geq 4$  lines);
- patients who received prior treatment of pertuzumab in addition to trastuzumab and T-DM1;
- patients who received at least one prior treatment with tyrosine kinase inhibitor (TKI) for HER2 (lapatinib and neratinib).

**5.4 Safety Analyses**

All safe analyses will be reported based on the Safety Population for each cohort.

### 5.4.1 Drug Exposure

The extent of exposure to poziotinib will be summarized with descriptive statistics using the following parameters:

- Duration of treatment: number of days between first dose and last dose of poziotinib, inclusive (i.e. days difference between first dose and last dose +1).
- Number of cycles treated
- Days of treatment administered
- Relative dose intensity (RDI): the percentage of planned dose that each patient actually received during the study. The planned dose is defined as the dose that would be given if no doses were missed and no dose reductions were made for the number of cycles (28 days per cycle) for the duration of treatment regardless of the number of cycles actually administered. Thus,

$$RDI = 100 * \frac{\text{total dose administered}}{336 * \left[ \text{integer of } \left( \frac{\text{days difference between first dose and last dose}}{21} \right) + 1 \right]}$$

- Last dose level: the last dose is assumed to be the lowest dose level prescribed by investigator
- Number of dose reduction
- Number and percentage of patients with no reduction, or with dose reduction to 16mg (Cohort 1 only), 12mg, 10mg and 8mg.
- Study day of first dose reduction
- Study day and duration of first drug interruption

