##### 6.1.3 Poziotinib Administration

Poziotinib is supplied as 8-mg and 2-mg tablets and will be administered orally once daily at approximately the same time each morning according to the schedule for each cohort during each 21-day cycle. If the morning dose is missed, this dose may be administered any time during the day, at least 8 hours prior to the next scheduled dose.

- **Cohort 1:** 24 mg (three 8-mg tablets) for 14 days and then 7 treatment-free rest days
- **Cohort 2:** 16 mg (two 8-mg tablets) once daily continuously
- **Cohort 3:** 12 mg (one 8-mg tablet and two 2-mg tablets) once daily continuously

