## 3 STUDY OVERVIEW

This is a Phase 2, open-label, multicenter study to establish the dose regimen and evaluate the preliminary efficacy and the safety / tolerability of poziotinib in approximately 75 patients with HER2-positive MBC who have received at least 2 prior HER2-directed treatment regimens including trastuzumab and T-DM1.

The Screening period (Day -30 to Day -1) lasts up to 30 days prior to Cycle 1, Day 1. Patients must meet all Inclusion/Exclusion Criteria to participate in the study. Eligible patients will provide written Informed Consent prior to undergoing any study procedures.

Each treatment cycle will be 21 days in duration. The original protocol contained only **Cohort 1**. In Amendment 1, patient enrollment in **Cohort 1** was complete, and new patients began enrollment into **Cohort 2**. **Cohort 2** was continued after two Safety Data Reviews and no patient was enrolled into additional cohorts.

**Cohort 1:** 24 mg (three 8-mg tablets once daily) for 2 weeks, rest 1 week

- 33 patients were enrolled into **Cohort 1** under original protocol.

**Cohort 2:** 16 mg (two 8-mg tablets once daily) continuous dosing

- Safety Data Review: Rate of Grade 3 or greater AEs of special interest (ie, diarrhea, skin rash, stomatitis) that are identified after the first 6 patients and again after 12 patients have completed **Cycle 1**:
  - **>33%:** Stop **Cohort 2** ( $\geq 3$  of 6 patients or  $\geq 5$  of 12 patients with Grade 3 or greater AEs of special interest) and begin **Cohort 3**.
  - **$\leq 33\%$ :** Keep enrolling **Cohort 2** until 30 patients are enrolled and treated and no additional patients will be enrolled.
- 34 patients were enrolled into **Cohort 2** under Amendment 1 or Amendment 2.

**Cohort 3:** 12 mg (one 8-mg tablet and two 2-mg tablet once daily) continuous dosing

- Only if **Cohort 2** is stopped due to toxicity.
- No patient was enrolled into **Cohort 3**.

Toxicity are assessed based on the grade of the adverse events using CTCAE Version 4.03.

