All treatments are taken orally, once daily (QD) at approximately the same time each morning. On Day 1 of each cycle, the patient's absolute neutrophil count (ANC) must be  $\geq 1.5 \times 10^9/L$  and platelet count must be  $\geq 100 \times 10^9/L$  before administering the next dose of poziotinib. For Cycle 1 only, the ANC and platelet levels should also be confirmed prior to the dose on Day 8. Day 1 of a new cycle is equivalent to Day 22 of the previous cycle, with a window of  $\pm 3$  days for the visit. If a visit is delayed during 1 cycle, then all subsequent cycles will be delayed sequentially.

All treated patients will be followed up until disease progression, death, intolerable adverse events or up to a maximum of 24 months whichever comes earlier.

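### The relative dose intensity definition in SAP 5.4.1 gives a 28-day cycle against a 21-day formula, and the formula scores fully adherent patients far below 100%

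*SAP*

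**What the plan says.** SAP 5.4.1 describes RDI as "the percentage of planned dose that each patient actually received during the study". Its benchmark is the full-schedule amount, with nothing skipped or lowered, "made for the number of cycles (28 days per cycle) for the duration of treatment regardless of the number of cycles actually administered". The same list defines duration of treatment as the "number of days between first dose and last dose of poziotinib, inclusive".

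The displayed formula is 100 × total dose administered, divided by 336 × [integer(days from first to last dose / 21) + 1].

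On the schedule, SAP section 3 says "Each treatment cycle will be 21 days in duration" and adds "If a visit is delayed during 1 cycle, then all subsequent cycles will be delayed sequentially". Protocol 6.1.3 gives Cohort 1 as "24 mg (three 8-mg tablets) for 14 days and then 7 treatment-free rest days" and Cohort 2 as 16 mg daily without a break. No patient entered Cohort 3.

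**The concern.** The cycle length in the text disagrees with the formula it introduces. SAP 5.1.5 relies on independent programming and on checking tables against the plan, and a programmer working from the words would not match one working from the formula.

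The second problem affects the values. If the benchmark is a full schedule over the time from first to last dose, a patient who missed nothing should score 100%. The denominator instead adds a whole cycle's dose as soon as a new 21-day period begins, so it can charge planned dose for up to 20 days after the last dose. The result mixes the date of the last dose, including stops for progression, with missed and reduced doses.

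RDI is the only exposure parameter in SAP 5.4.1 that sets dose received against dose planned. Establishing the dosing schedule is a primary objective and tolerability a secondary one, so readers will look at it.

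**Working it through.** **Inputs.** Cohort 1: 24 mg on days 1–14 of 21; Cohort 2: 16 mg every day (Protocol 6.1.3). Cycle length: 21 days (SAP section 3, Protocol 3.1). Formula: SAP 5.4.1.

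**The constant 336.** Cohort 1: 24 × 14 = 336 mg. Cohort 2: 16 × 21 = 336 mg. The plan's figure is reproduced and fits 21 days. A 28-day cycle would need 16 × 28 = 448 mg in Cohort 2. Putting 28 into the formula does not work either: with 336 mg, a fully adherent Cohort 2 patient with last dose on day 28 scores 448/336 = 133.3%; with 448 mg, one completed 21-day cycle scores 336/448 = 75.0%.

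**Fully adherent patients under the formula.** Assume exact 21-day cycles, nothing missed or reduced, and last dose on day D, so the days difference is D − 1. Placing the +1 inside or outside the integer function gives the same value.

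- Cohort 2: RDI = 100 × 16D / (336 × [integer((D − 1)/21) + 1])
- Cohort 1: the same denominator; dose = 24 × (14 × full cycles + dosing days in the last cycle)

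| Last dose | Cohort 1 | Cohort 2 |
|---|---|---|
| Day 14 | 336/336 = 100% | 224/336 = 66.7% |
| Day 21 | rest week | 336/336 = 100% |
| Day 22 | 360/672 = 53.6% | 352/672 = 52.4% |
| Day 43 | 696/1008 = 69.0% | 688/1008 = 68.3% |

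The score is 100% only when the last dose is the last one scheduled in a cycle.

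**Largest shortfall in cycle k** (last dose on the first day of the cycle): (20/21)/k in Cohort 2 and (13/14)/k in Cohort 1.

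| Cycle | Cohort 2, points | Cohort 1, points |
|---|---|---|
| 2 | 47.6 | 46.4 |
| 3 | 31.7 | 31.0 |
| 5 | 19.0 | 18.6 |
| 9 | 10.6 | 10.3 |

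**What 52.4% can mean.** A Cohort 2 patient treated to day 42 who missed 20 of 42 doses scores 22 × 16/672 = 52.4%. This equals the score of the patient who took all 22 doses and stopped on day 22.

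**Between cohorts.** With exact cycles, Cohort 2 never scores above Cohort 1 for the same stop day; the largest gap is 33.3 points (day 14). The average gap depends on when patients stop, which the documents do not give.

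- Stops spread evenly over calendar days, Cohort 1 against Cohort 2: 14.5/21 = 69.0% against 11/21 = 52.4% in cycle 1; 93.8% against 90.5% in cycle 5.
- Last doses spread evenly over each cohort's own dosing days: 7.5/14 = 53.6% against 52.4% in cycle 1; 90.7% against 90.5% in cycle 5.
- Late cycle starts can reverse the order. If each Cohort 1 cycle starts 3 days late, the fourth cycle's last dose falls on day 24 × 3 + 14 = 86. All doses were taken, but five periods are charged: 4/5 = 80.0%. Cohort 2 dosed without interruption to day 86 scores 1376/1680 = 81.9%.

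No net direction between cohorts follows.

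**The case against.** The strongest reply is that whole-cycle charging was intended. The planned dose is tied to a number of cycles, whatever number was actually given, and the formula counts the 21-day periods started. On that reading the two patients at 52.4% are rightly equal: each received 22 of the 42 doses in the two cycles charged. The 28 is then a slip with no effect, and the rest is a choice of definition. Proration has its own blind spot, since a patient who stops for good on day 3 would score 100%. The largest shortfalls arise from early stops just after a cycle starts, and SAP 5.4.1 also reports duration, cycles, reductions and interruptions. RDI does not appear among the safety summaries in Protocol 8.6.

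Much of this stands. The wording allows the whole-cycle reading, so the second part is a rule that gives a misleading result and not a slip in calculation. The effect fades with longer treatment, and no typical size can be given.

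It does not rescue the measure. Under whole-cycle charging, taking one more scheduled dose on day 22 still cuts a perfect score roughly in half. The other exposure summaries help interpret a low value but do not correct it. Stops just after a cycle starts are also plausible: Protocol 5.4.6 requires samples before and after a dose on Day 1 of Cycles 2 and 3, and Protocol 5.3.7 lists tumor assessment under the Cycle 3+ Day 1 visit. A patient dosed on day 43 and stopped for progression found then scores 68.3% or 69.0% with perfect adherence.

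**Conclusion.** Both parts hold. The 28-day wording contradicts the formula, the SAP overview and the protocol, and changes no number. The uncharged-for-time problem is the substantive one: the formula gives fully adherent patients scores well below 100% in both cohorts, by up to 47.6 points in cycle 2 and about 10 points in cycle 9. These sizes assume exact 21-day cycles and no missed or reduced dose; how often patients stop at unfavourable points is not known from the documents.

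This should be fixed, but its reach is limited. RDI is descriptive, and the objective response rate, the Cohort 2 enrollment rule and the primary safety outcomes do not depend on it.

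**What to change.** 1. Change 28 to 21 in the planned-dose text.
2. Keep 336 mg for each completed 21-day period between first and last dose, and prorate only the last period to the last dose date, using each cohort's existing schedule. For Cohort 2 this is 16 mg × days elapsed in the period; for Cohort 1 it is 24 mg × the smaller of days elapsed and 14. With fixed 21-day cycles, every fully adherent patient then scores exactly 100% on any stop day.
3. State how cycle starts that are delayed or moved within the ±3-day window are counted, because proration does not remove every such effect. In Cohort 1, a second cycle started and stopped on day 25 scores 360/672 = 53.6% now and 360/432 = 83.3% prorated; on day 19 it scores 360/336 = 107.1% either way. The day-86 example moves from 80.0% to 1344/(1344 + 24 × 2) = 96.6%.
4. Keep the whole-cycle version as a supplementary summary, labelled as such, because under proration the doses forgone after a permanent mid-cycle stop no longer lower RDI.

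The cost is one phrase, one formula with its program, and one sentence on shifted cycles. The dose dates are already inputs to the current formula, so trial conduct and data collection do not change.
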